10.3.5 Reporting of AE, SAE, and Other Reportable Safety Events to the Sponsor

AE, SAE, and other reportable safety event reporting to Sponsor via electronic data collection tool

- The primary mechanism for reporting to the Sponsor will be the electronic data collection (EDC) tool.
 - Electronic reporting procedures can be found in the EDC data entry guidelines (or equivalent).
 - If the electronic system is unavailable for more than 24 hours, then the site will use the paper AE Reporting form.
 - Reference Section 8.4.1 for reporting time requirements.
- The site will enter the SAE data into the electronic system as soon as it becomes available.
- After the study is completed at a given site, the EDC tool will be taken off-line to prevent the entry of new data or changes to existing data.
- If a site receives a report of a new SAE from a study participant or receives updated data on a previously reported SAE after the EDC tool has been taken off-line, then the site can report this information on a paper SAE form or by telephone (see next section).
- Contacts for SAE reporting can be found in the Investigator Study File Binder (or equivalent).

SAE reporting to the Sponsor via paper CRF

- If the EDC tool is not operational, facsimile transmission or secure e-mail of the SAE paper CRF is the preferred method to transmit this information to the Sponsor.
- In rare circumstances and in the absence of facsimile equipment, notification by telephone is acceptable with a copy of the SAE data collection tool sent by overnight mail or courier service.
- Initial notification via telephone does not replace the need for the investigator to complete and sign the SAE CRF pages within the designated reporting time frames.
- Contacts and instructions for SAE reporting and paper reporting procedures can be found in the Investigator Study File Binder (or equivalent).

10.4 Appendix 4: Medical Device Incidents: Definition and Procedures for Recording, Evaluating, Follow-up, and Reporting

This appendix is not applicable for this study.

10.5 Appendix 5: Contraceptive Guidance and Pregnancy Testing

10.5.1 Definitions

Women of Childbearing Potential (WOCBP)

A woman is considered fertile following menarche and until becoming postmenopausal unless permanently sterile.

Women in the following categories are not considered WOCBP:

- Premenarchal
- Premenopausal female with 1 of the following:
 - Documented hysterectomy
 - Documented bilateral salpingectomy
 - Documented bilateral oophorectomy

Note: Documentation can come from the site personnel's review of the participant's medical records, medical examination, or medical history interview.

- Postmenopausal female
 - A postmenopausal state is defined as no menses for 12 months without an alternative medical cause.
 - A high follicle stimulating hormone (FSH) level in the postmenopausal range may be used to confirm a postmenopausal state in women not using hormonal contraception or hormone replacement therapy (HRT). However, in the absence of 12 months of amenorrhea, confirmation with 2 FSH measurements in the postmenopausal range is required.
 - Females on HRT and whose menopausal status is in doubt will be required to use 1 of the nonhormonal highly effective contraception methods if they wish to continue their HRT during the study. Otherwise, they must discontinue HRT to allow confirmation of postmenopausal status before study enrollment.

10.5.2 Contraception Requirements

Male Participants

Male participants are not required to use a form of contraception.

Female Participants

Female participants of childbearing potential are eligible to participate if they agree to use 1 of the contraception methods described in [Table 5](#) consistently and correctly during the protocol-defined time frame in Section 5.1.

Table 5 Contraceptive Methods

Highly Effective Contraceptive Methods That Are User Dependent^a Failure rate of <1% per year when used consistently and correctly.
● Combined (estrogen- and progestogen- containing) hormonal contraception 
○ Oral
● Progestogen only hormonal contraception 
○ Oral
Highly Effective Methods That Have Low User Dependency Failure rate of <1% per year when used consistently and correctly.
● Intrauterine hormone-releasing system (IUS)
● Intrauterine device (IUD)
● Bilateral tubal occlusion
● Vasectomized partner A vasectomized partner is a highly effective contraception method provided that the partner is the sole male sexual partner of the WOCBP and the absence of sperm has been confirmed. If not, an additional highly effective method of contraception should be used.
● Sexual abstinence Sexual abstinence is considered a highly effective method only if defined as refraining from heterosexual intercourse during the entire period of risk associated with the study intervention. The reliability of sexual abstinence needs to be evaluated in relation to the duration of the study and the preferred and usual lifestyle of the participant.
Notes: ^a Typical use failure rates are higher than perfect-use failure rates (ie, when used consistently and correctly).

10.5.3 Pregnancy Testing

WOCBP should only be included after a negative highly sensitive urine or serum pregnancy test.

Pregnancy testing will be performed at Visit 1 (in WOCBP) and after Visit1 whenever an expected menstrual cycle is missed or when pregnancy is otherwise suspected.

10.6 Appendix 6: Collection and Management of Specimens for Future Biomedical Research

1. Definitions

- a) Biomarker: A biological molecule found in blood, other body fluids, or tissues that is a sign of a normal or abnormal process or of a condition or disease. A biomarker may be used to see how well the body responds to a treatment for a disease or condition.
- b) Pharmacogenomics: The investigation of variations of DNA and RNA characteristics as related to drug/vaccine response.²
- c) Pharmacogenetics: A subset of pharmacogenomics, pharmacogenetics is the influence of variations in DNA sequence on drug/vaccine response.²
- d) DNA: Deoxyribonucleic acid.
- e) RNA: Ribonucleic acid.

2. Scope of Future Biomedical Research

The specimens consented and/or collected in this study as outlined in Section 8.9 will be used in various experiments to understand:

- The biology of how drugs/vaccines work
- Biomarkers responsible for how a drug/vaccine enters and is removed by the body
- Other pathways drugs/vaccines may interact with
- The biology of disease

The specimen(s) may be used for future assay development and/or drug/vaccine development.

It is now well recognized that information obtained from studying and testing clinical specimens offers unique opportunities to enhance our understanding of how individuals respond to drugs/vaccines, enhance our understanding of human disease and ultimately improve public health through development of novel treatments targeted to populations with the greatest need. All specimens will be used by the Sponsor or those working for or with the Sponsor.

3. Summary of Procedures for Future Biomedical Research.

a) Participants for Enrollment

All participants enrolled in the clinical study will be considered for enrollment in the future biomedical research substudy

b) Informed Consent

Informed consent for specimens (ie, DNA, RNA, protein, etc.) will be obtained during screening for protocol enrollment from all participants or legal guardians, at a study visit by the investigator or his or her designate. Informed consent for future biomedical research should be presented to the participants on the visit designated in the SoA. If delayed, present consent at next possible Participant Visit. Consent forms signed by the participant will be kept at the clinical study site under secure storage for regulatory reasons.

A template of each study site's approved informed consent will be stored in the Sponsor's clinical document repository.

c) eCRF Documentation for Future Biomedical Research Specimens

Documentation of participant consent for future biomedical research will be captured in the eCRFs. Any specimens for which such an informed consent cannot be verified will be destroyed.

d) Future Biomedical Research Specimen(s)

Collection of specimens for future biomedical research will be performed as outlined in the SoA. In general, if additional blood specimens are being collected for future biomedical research, these will usually be obtained at a time when the participant is having blood drawn for other study purposes.

4. Confidential Participant Information for Future Biomedical Research

In order to optimize the research that can be conducted with future biomedical research specimens, it is critical to link participant' clinical information with future test results. In fact little or no research can be conducted without connecting the clinical study data to the specimen. The clinical data allow specific analyses to be conducted. Knowing participant characteristics like gender, age, medical history and treatment outcomes are critical to understanding clinical context of analytical results.

To maintain privacy of information collected from specimens obtained for future biomedical research, the Sponsor has developed secure policies and procedures. All specimens will be single-coded per ICH E15 guidelines as described below.

At the clinical study site, unique codes will be placed on the future biomedical research specimens. This code is a random number which does not contain any personally identifying information embedded within it. The link (or key) between participant identifiers and this unique code will be held at the study site. No personal identifiers will appear on the specimen tube.

5. Biorepository Specimen Usage

Specimens obtained for the Sponsor will be used for analyses using good scientific practices. Analyses utilizing the future biomedical research specimens may be performed by the Sponsor, or an additional third party (eg, a university investigator) designated by the Sponsor. The investigator conducting the analysis will follow the Sponsor's privacy and confidentiality requirements. Any contracted third party analyses will conform to the specific scope of analysis outlined in this substudy. Future biomedical research specimens remaining with the third party after specific analysis is performed will be reported to the Sponsor.

6. Withdrawal From Future Biomedical Research

Participants may withdraw their consent for future biomedical research and ask that their biospecimens not be used for future biomedical research. Participants may withdraw consent at any time by contacting the principal investigator for the main study. If medical records for the main study are still available, the investigator will contact the Sponsor using the designated mailbox ([contact]).

Subsequently, the participant's specimens will be flagged in the biorepository and restricted to main study use only. If specimens were collected from study participants specifically for future biomedical research, these specimens will be removed from the biorepository and destroyed. Documentation will be sent to the investigator confirming withdrawal and/or destruction, if applicable. It is the responsibility of the investigator to inform the participant of completion of the withdrawal and/or destruction, if applicable. Any analyses in progress at the time of request for withdrawal/destruction or already performed prior to the request being received by the Sponsor will continue to be used as part of the overall research study data and results. No new analyses would be generated after the request is received.

In the event that the medical records for the main study are no longer available (eg, if the investigator is no longer required by regulatory authorities to retain the main study records) or the specimens have been completely anonymized, there will no longer be a link between the participant's personal information and their specimens. In this situation, the request for withdrawal of consent and/or destruction cannot be processed.

7. Retention of Specimens

Future biomedical research specimens will be stored in the biorepository for potential analysis for up to 20 years from the end of the main study. Specimens may be stored for longer if a regulatory or governmental authority has active questions that are being answered. In this special circumstance, specimens will be stored until these questions have been adequately addressed.

Specimens from the study site will be shipped to a central laboratory and then shipped to the Sponsor-designated biorepository. If a central laboratory is not utilized in a particular study, the study site will ship directly to the Sponsor-designated biorepository. The specimens will be stored under strict supervision in a limited access facility which

operates to assure the integrity of the specimens. Specimens will be destroyed according to Sponsor policies and procedures and this destruction will be documented in the biorepository database.

8. Data Security

Databases containing specimen information and test results are accessible only to the authorized Sponsor representatives and the designated study administrator research personnel and/or collaborators. Database user authentication is highly secure, and is accomplished using network security policies and practices based on international standards to protect against unauthorized access.

9. Reporting of Future Biomedical Research Data to Participants

No information obtained from exploratory laboratory studies will be reported to the participant, family, or physicians. Principle reasons not to inform or return results to the participant include: Lack of relevance to participant health, limitations of predictive capability, and concerns regarding misinterpretation.

If important research findings are discovered, the Sponsor may publish results, present results in national meetings, and make results accessible on a public website in order to rapidly report this information to doctors and participants. Participants will not be identified by name in any published reports about this study or in any other scientific publication or presentation.

10. Future Biomedical Research Study Population

Every effort will be made to recruit all participants diagnosed and treated on Sponsor clinical studies for future biomedical research.

11. Risks Versus Benefits of Future Biomedical Research

For future biomedical research, risks to the participant have been minimized and are described in the Future Biomedical Research informed consent.

The Sponsor has developed strict security, policies, and procedures to address participant data privacy concerns. Data privacy risks are largely limited to rare situations involving possible breach of confidentiality. In this highly unlikely situation, there is risk that the information, like all medical information, may be misused.

12. Questions

Any questions related to the future biomedical research should be emailed directly to [contact].

13. References

- 1) National Cancer Institute [Internet]: Available from <https://www.cancer.gov/publications/dictionaries/cancer-terms?cdrid=45618>
- 2) International Conference on Harmonization [Internet]: E15: Definitions for Genomic Biomarkers, Pharmacogenomics, Pharmacogenetics, Genomic Data and Sample Coding Categories. Available from <http://www.ich.org/products/guidelines/efficacy/efficacy-single/article/definitions-for-genomic-biomarkers-pharmacogenomics-pharmacogenetics-genomic-data-and-sample-cod.html>
- 3) Industry Pharmacogenomics Working Group [Internet]: Understanding the Intent, Scope and Public Health Benefits of Exploratory Biomarker Research: A Guide for IRBs/IECs and Investigational Site Staff. Available at <http://i-pwg.org/>
- 4) Industry Pharmacogenomics Working Group [Internet]: Pharmacogenomics Informational Brochure for IRBs/IECs and Investigational Site Staff. Available at <http://i-pwg.org/>

10.7 Appendix 7: Country-specific Requirements

This appendix is not applicable to this study.

10.8 Appendix 8: Abbreviations

Abbreviation	Expanded Term
AE	adverse event
ALP	alkaline phosphatase
ALT (SGPT)	alanine aminotransferase (serum glutamic pyruvic transaminase)
APaT	all participants as treated
AST (SGOT)	aspartate aminotransferase (serum glutamic oxaloacetic transaminase)
ATP	adenosine triphosphate
BID	twice daily
β-hCG	beta-human chorionic gonadotropin
CFR	Code of Federal Regulations
CI	confidence interval
CONSORT	Consolidated Standards of Reporting Trials
CRF	Case Report Form
CSD	Cough Severity Diary
CT	computed tomography
DILI	drug-induced liver injury
DNA	deoxyribonucleic acid
ECG	electrocardiogram
ECI	event of clinical interest
EQ5D-5L	EuroQoL 5 Version Five Dimensions Questionnaire
eCRF	electronic Case Report Form
EDC	electronic data collection
eGFR	estimated glomerular filtration rate
EMA	European Medicines Agency
FAS	full analysis set
FDAAA	Food and Drug Administration Amendments Act
FEV ₁	forced expiratory volume in 1 second
FSH	follicle stimulating hormone
FVC	forced vital capacity
GCP	Good Clinical Practice
GERD	gastroesophageal reflux disease
HIV	human immunodeficiency virus
HRQoL	health-related quality of life
HRT	hormone replacement therapy
IB	Investigator's Brochure
ICF	Informed Consent Form
ICH	International Conference on Harmonization
IEC	Independent Ethics Committee
IMP	investigational medical product
IRB	Institutional Review Board
IUD	intrauterine device
IUS	intrauterine hormone-releasing system
JRS	the Japanese Respiratory Society
LCQ	Leicester Cough Questionnaire
MCH	mean corpuscular hemoglobin
MCV	mean corpuscular volume
NA	not applicable
NIMP	non investigational medical product
PGIC	Patient Global Impression of Change
PRO	patient reported outcome

Abbreviation	Expanded Term
RBC	red blood cell (count)
RNA	ribonucleic acid
SAE	serious adverse event
SD	standard deviation
SLAB	supplemental laboratory tests
SoA	schedule of activities
sSAP	supplemental Statistical Analysis Plan
SUSAR	suspected unexpected serious adverse reaction
TC	telephone contact
V	visit
WBC	white blood cell (count)
WOCBP	women of child bearing potential

1.0 INTRODUCTION

This supplemental SAP (sSAP) is a companion document to the protocol. In addition to the information presented in the protocol SAP which provides the principal features of analyses for this trial, this supplemental SAP provides additional sensitivity statistical analysis details, data derivations and documents modifications or additions to the analysis plan that are not “principal” in nature and result from information that was not available at the time of protocol finalization.

2.0 SUMMARY OF CHANGES

[14-Apr-2020 Amendment 2]

Sections 3.1 and 3.7

The scope of the interim analysis of safety data was expanded to include all available data up to the cutoff date for the interim database lock.

[13-Feb-2020 Amendment 1]

Section 3.6.1

The covariance structure for the longitudinal analysis of covariance was changed from Toeplitz to unstructured.

Analysis of EQ VAS was added.

Section 3.11

It was clarified that the “Number of Days Should Be on Therapy” is the total number of days from the first scheduled treatment day to the last dose day for those participants who discontinued *study medication* permanently, instead of for those participants who discontinued the *study* permanently.

Appendix

The relative day ranges for body weight was modified to include the additional timepoints (Visits 3 and 6) included in the protocol amendment (038-01).

3.0 ANALYTICAL AND METHODOLOGICAL DETAILS

3.1 Statistical Analysis Plan Summary

Key elements of the statistical analysis plan are summarized below; the comprehensive plan is provided in Sections 3.2-3.12.

Study Design Overview	Phase 3 study, Randomized, Double-blind Clinical Study to Evaluate the Long-term Safety and Efficacy of MK-7264 in Japanese Adult Participants with Refractory or Unexplained Chronic Cough
Treatment Assignment	Participants will be randomized in a 1:1 ratio to either MK-7264 45 mg BID or MK-7264 15 mg BID.
Analysis Populations	Efficacy: Full Analysis Set (FAS) population. Safety: All Participants as Treated (APaT) population.
Primary Endpoint	
• Adverse events (AEs)• Study treatment discontinuations due to AE
Statistical Methods for Key Efficacy Analyses	Change from baseline in LCQ total score at Week 12 and through Week 52 will be analyzed using the longitudinal analysis of covariance (ANCOVA) model. The model will include terms for treatment, visit, the interactions of treatment by visit, and baseline value as covariates. The change from baseline to each visit and 95% CIs will be estimated from this model.
Statistical Methods for Key Safety Analyses	AEs will be summarized by the number and percentage of the participants who experienced respective events. Change from baseline in laboratory tests, vital signs at respective timepoints will be summarized by descriptive statistics.
Interim Analyses	The planned interim efficacy analysis will be performed based on the data up to Week 24 when all the randomized participants have completed Week 24 or discontinued prior to Week 24. Safety analysis will include all available data up to the cutoff date for the interim database lock.
Multiplicity	No multiplicity adjustment is planned in this trial.
Sample Size and Power	A total of 160 participants will be enrolled. Assuming a discontinuation rate of approximately 47% at Week 52, 84 participants are expected to complete 52 weeks of treatment.

3.2 Responsibility for Analyses / In-house Blinding

The statistical analysis of the data obtained from this study will be the responsibility of the Sponsor.

This study will be conducted as a double-blind study under in-house blinding procedures. Double blinding technique with in-house blinding will be used until all the randomized participants have completed Week 24 or discontinued prior to Week 24 after which a double blinding only technique will be used. The official, final database will not be unblinded until medical/scientific review has been performed, protocol deviations have been identified, and data have been declared final and complete.

The Clinical Biostatistics department will generate the randomized allocation schedule(s) for study treatment assignment.

3.3 Hypotheses / Estimation

There are no hypotheses for this study.

3.4 Analysis Endpoints

3.4.1 Efficacy Endpoints

- Leicester Cough Questionnaire (LCQ) total score
- Mean weekly Cough Severity Diary (CSD) total score
- EuroQoL 5 Version Five Dimension Questionnaire (EQ5D-5L)
- Patient Global Impression Change (PGIC)

3.4.2 Safety Endpoints

- Adverse event (AE)
- Study treatment discontinuations due to AE
- Laboratory test
- Vital sign
- Taste related AE
- Oral paraesthesia/hypoesthesia

3.5 Analysis Populations

3.5.1 Efficacy Analysis Population

The FAS population will serve as the primary population for the analysis of efficacy data in this study. The FAS population consists of all randomized participants who have taken at least one dose of study medication and provided at least one baseline and one post-baseline endpoint observations during the treatment period.

Participants will be included in the treatment group to which they are randomized for the analysis of efficacy data using the FAS populations.

3.5.2 Safety Analysis Populations

The APaT population will be used for the analysis of safety data in this study. The APaT population consists of all randomized participants who received at least one dose of study treatment. Participants will be included in the treatment group corresponding to the study treatment they actually received for the analysis of safety data using the APaT population. Discontinued participants before Week 52 will be included in APaT population. For most participants this will be the treatment group to which they are randomized. Participants who take incorrect study treatment for the entire treatment period will be included in the treatment group corresponding to the study treatment actually received.

If a participant is found to have taken one or more incorrect doses of study medication from that to which he/she was randomized, then the participant will be counted in the higher dose arm he/she actually received; that is, if a participant was originally randomized to MK-7264 15 mg but during the course of the study has taken 1 or more doses of MK-7264 45 mg, then the participant will be included in the MK-7264 45 mg treatment arm in the safety analysis.

At least one laboratory or vital sign measurement obtained subsequent to at least one dose of study treatment is required for inclusion in the analysis of each specific parameter. To assess change from baseline, a baseline measurement is also required.

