8.1.8 Study Intervention Administration

Since MK-7264 45 mg and 15 mg will differ in appearance and have corresponding matching placebos, participants will receive two study intervention bottles for the treatment period (ie, either MK-7265 45 mg and placebo matched to MK-7264 15 mg OR MK-7264 15 mg and placebo matched to MK-7264 45 mg). Participant should be instructed to take one tablet from each bottle BID.

Participants will be provided with enough study intervention to last between study site visits. Prescription and distribution of study interventions are allowed at unscheduled visits as well as scheduled visits.

The first dose of study intervention will be administered at the study site at Visit 2 after completing baseline assessments. Subsequent dosing will be performed by the participant (ie, unsupervised at his/her home) BID, approximately 12 hours apart at approximately the same time each day. The last dose will be on the day before Visit 8.

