9.5.2 Safety Analysis Population

The APaT population will be used for the analysis of safety data in this study. The APaT population consists of all randomized participants who received at least one dose of study treatment. Participants will be included in the treatment group corresponding to the study treatment they actually received for the analysis of safety data using the APaT population. Discontinued participants before Week 52 will be included in APaT population. For most participants this will be the treatment group to which they are randomized. Participants who take incorrect study treatment for the entire treatment period will be included in the treatment group corresponding to the study treatment actually received.

At least one laboratory or vital sign measurement obtained subsequent to at least one dose of study treatment is required for inclusion in the analysis of each specific parameter. To assess change from baseline, a baseline measurement is also required.

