3.6 Statistical Methods

The results will be provided by treatment group and total (combined treatment group). There is no plan to do between treatment group comparisons.

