3.11 Compliance (Medication Adherence)

For each participant, percent compliance will be calculated using the following formula:

$$\text{Percent Compliance} = \frac{\text{Number of Days on Therapy}}{\text{Number of Days Should Be on Therapy}} \times 100\%$$

A day within the study will be considered an “On-Therapy” day if the participant takes all required medication as instructed in Section 8 of the Protocol – Study Assessments and Procedures. When a participant takes less than or more than the required medication on a day, that day is not considered an On-Therapy day.

For participants who are followed for the entire study period, the “Number of Days Should Be on Therapy” is the total number of days from the first scheduled treatment day to the last scheduled treatment day. For participants who discontinue from the study medication permanently, the “Number of Days Should Be on Therapy” is the total number of days from the first scheduled treatment day to the last dose day.

Summary statistics will be provided on percent compliance for the APaT population.

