3.12 Extent of Exposure

The duration of treatment for each participant will be evaluated by calculating the number of days on therapy. Exposure to study medication will be summarized using descriptive statistics (mean, SD, median, minimum, and maximum) for the APaT population.

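### Does counting a mixed-dose participant wholly under 45 mg, with no day-by-dose exposure count, spoil the by-dose safety results?

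*Combined protocol and SAP*

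**What the plan says.** Protocol 9.5.2 places participants in the safety population by the treatment they received. The only dosing error it spells out is the complete one: "Participants who take incorrect study treatment for the entire treatment period will be included in the treatment group corresponding to the study treatment actually received". sSAP 3.5.2 repeats that sentence and adds a rule for partial errors. A participant found to have taken any incorrect dose is placed by the highest dose received: "then the participant will be counted in the higher dose arm he/she actually received". The worked example is a 15 mg participant who "has taken 1 or more doses of MK-7264 45 mg, then the participant will be included in the MK-7264 45 mg treatment arm".

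For exposure, sSAP 3.12 says "The duration of treatment for each participant will be evaluated by calculating the number of days on therapy" and "Exposure to study medication will be summarized using descriptive statistics (mean, SD, median, minimum, and maximum) for the APaT population". Protocol 9.12 says the same. sSAP 3.6 gives results by treatment group and combined, and plans no comparison between groups. sSAP 3.11 defines a day on therapy for the compliance calculation: "When a participant takes less than or more than the required medication on a day, that day is not considered an On-Therapy day". On supply, protocol 8.1.8 says "Participants will be provided with enough study intervention to last between study site visits".

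Neither document plans a table of days by dose actually taken, a listing of mixed-dose participants, or a safety display by randomised arm.

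**The concern.** The study's main purpose is long-term safety, shown for each dose and combined, and protocol 4.3.1 says that the most common adverse event is dose related. Attribution to dose therefore matters.

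A 15 mg participant holds only 15 mg tablets and placebo, so a 45 mg dose implies a supply or dispensing error. One such dose moves the whole participant, including all 15 mg days, into the 45 mg column. Events that began on 15 mg before the error move too. For a rare or serious event, one record could decide which dose appears to carry it. The reverse error has a similar effect: a 45 mg participant who takes 15 mg for a time stays under 45 mg, so those 15 mg days are also shown there.

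Two further points seemed to add to this. If the required medication in sSAP 3.11 is judged by strength, the 45 mg days might not count at all, and the 45 mg column would hold only this participant's 15 mg days. Also, the partial-error rule stands in the sSAP but not in the protocol.

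**Working it through.** **The plan's own figures.** Protocol 9.9 and sSAP 3.9 expect 84 completers from 160 at about 47% discontinuation: 160 × 0.53 = 84.8, and 84/160 is 47.5% discontinuation exactly. The zero-event upper 95% bounds are 1 − 0.025^(1/84) = 4.3% and 1 − 0.025^(1/42) = 8.4%. Both match the text, and the concern disturbs none of these figures.

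**One participant's days.** Site visits fall on Days 1, 28, 56, 84, 168, 266 and 365 (protocol 1.3). The intervals are 27, 28, 28, 84, 98 and 99 days, which sum to 364.

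- One stray 45 mg day in a completer leaves 364 − 1 = 363 days at 15 mg inside the 45 mg column.
- An error assumed to last one scheduled interval leaves 364 − 27 = 337 down to 364 − 99 = 265 days (93% to 73%).

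The second range is an illustration. The rule is triggered by a single dose, and supply may be dispensed at unscheduled visits. The telephone contacts may also be held as site visits, which would shorten the intervals. The 364 days apply only to completers.

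**The planned summary.** sSAP 3.12 reports arm-level statistics, so the arm mean is the figure to check. Inputs: 80 per arm, 42 completers at 364 days, and 38 dropouts at an assumed mean of *d* days.

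- Arm total: T = 42 × 364 + 38*d*
- Mean before the move: T/80
- 45 mg mean after moving one completer: (T + 364)/81
- 15 mg mean after moving one completer: (T − 364)/79

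| *d* | T | Mean before | 45 mg after | 15 mg after |
|---|---|---|---|---|
| 42 | 16,884 | 211.1 | 212.9 (+1.9) | 209.1 (−1.9) |
| 84 | 18,480 | 231.0 | 232.6 (+1.6) | 229.3 (−1.7) |
| 182 | 22,204 | 277.6 | 278.6 (+1.1) | 276.5 (−1.1) |

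Completers shown per arm go from 42 and 42 to 43 and 41. The combined column is the same in every row.

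**Adverse event percentages.** Moving one participant changes the 45 mg percentage by at most 1/81 − 0/80 = +1.2 points, or 80/81 − 80/80 = −1.2 points. At an assumed 48/80 (60%), the result is 49/81 = 60.5% or 48/81 = 59.3%. sSAP 3.6.2 reports numbers and percentages of participants, so misplaced exposure days are not the denominator of any planned event rate.

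**A rare event that began on 15 mg.** The 45 mg arm goes from 0/80 to 1/81 and the 15 mg arm from 1/80 to 0/79; combined stays 1/160. The exact upper 95% limits would go from 4.5% to 6.7% and from 6.8% to 4.6%. sSAP 3.6.2 plans no such limits. They appear only in the sample size section, so the planned table changes by one participant.

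**Tablet count or strength.** sSAP 3.11 refers to protocol Section 8 for what is required. Section 8.1.8 gives the instruction in tablets (one from each of two bottles, twice a day), and Section 8.5 counts overdose in tablets per bottle. A participant with a wrong bottle who follows the instruction is therefore on therapy, and the reading by strength falls away. sSAP 3.12 also does not say that it uses the 3.11 definition.

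**Protocol against sSAP.** sSAP 1.0 says that it adds detail to the protocol's plan. Protocol 9.5.2 leaves partial errors open and sSAP 3.5.2 fills the gap. The two do not conflict.

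**The case for a change.** The best case for a change is that attribution to dose is a primary output and that the interim results support a regulatory filing (protocol 4.1). The highest-dose rule is usually defended as cautious for the higher dose, but it also takes an event away from the lower dose. Having foreseen mixed dosing, the sSAP might as well say how those days and events are shown, which would cost a few sentences and avoid a choice made after unblinding. Errors could also cluster, for example through a wrong batch of kits. On the same assumptions, five moved completers with one stray day each would raise the 45 mg mean by 5.1 to 9.0 days and lower the 15 mg mean by 5.8 to 10.2 days. Between 7.6% and 9.7% of the 45 mg arm's days (5 × 363 over T + 5 × 364) would then have been taken at 15 mg.

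It stands that no by-dose display is planned and that, for one participant, the misplacement can be almost total. The step from there to a needed change does not stand. The rule applies only to someone found to have taken a wrong dose, so the affected participants are known by the time it is used. Safety is judged by clinical review of all relevant data (sSAP 3.6.2), not by a column count alone. Protocol deviations are identified before the final database is unblinded (sSAP 3.2). A cluster of errors would itself be a reportable conduct problem, described with its dates and doses. Repeating the adverse event summaries by randomised arm for one participant, worth at most 1.2 points, would be out of proportion.

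**Conclusion.** No change is needed. The sSAP uses an accepted rule for arm membership, states it in advance, and applies it in both directions of error. Followed as written, the plan gives sound safety results. What is missing is a display detail for an event that may never happen, and an analyst with such a case would list the participant's days and adverse events by dose and date.

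Per mixed-dose completer moved from 15 mg to 45 mg, the effect is about 1 to 2 days on an arm's mean exposure and at most 1.2 percentage points on an adverse event percentage in the 45 mg arm. The combined column does not move. If no error occurs, the effect is zero. These sizes rest on 80 participants and 42 completers per arm, dropouts leaving on average between Day 42 and Day 182 (assumed), and one affected participant. The documents give no rate of dosing errors, so the expected number cannot be stated. Only a cluster of errors would make the by-dose exposure figures noticeably misleading.
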